## **5.7 Study Drug Dose and Administration**

Complete instructions for dispensing and administering study drug are presented in the study specific Pharmacy Manual.

The subject will be instructed to take all study drug doses at home except when study drug will be administered in the clinic (ie, at the Days 1 and 3, and Weeks 2, 4, 8 and 12 visits). The subject will be instructed to take the study drug approximately at the same time every day (ie, orally in the morning after fasting overnight for a minimum of 8 hours). If a subject forgets to take their study drug at their scheduled time, the dose may be taken later that day following a minimum of 4 hours fast; however, no more than 1 dose should be taken on any calendar day and a minimum of 16 hours between doses should be maintained.

Stopping rules for study drug administration are provided in Section 10.1.

### **5.7.1 Dispensing of Study Drug**

When drug is dispensed at the clinic, study drug may be dispensed only under the supervision of a qualified pharmacist or an authorized designee and only for administration to the study subjects.

A 4-week supply of blinded study drug in individually labelled bottles will be dispensed by qualified site personnel to the subject at the visit on Day 1, Week 4, and 8. The bottle number dispensed to the subject and the number of tablets dispensed will be recorded in the site source documents. Subjects will be instructed to store study drug in the original bottle under refrigerated conditions. Subjects will be provided with a cooler bag to bring the study drug home. Once returning home, the subject will be instructed to refrigerate the study medication, removing it only for dosing.

### **5.7.2 Treatment Compliance**

The subject will be instructed to bring all study drug (including empty bottles) to the clinic at each study visit. Both accountability and study drug compliance will be reviewed at each visit as indicated in the SoA (Appendix 1). The number of tablets will be counted and the study personnel will ask the subjects why any doses were missed, if applicable. Any potential reasons for lack of compliance with dosing will be monitored and followed up by the study personnel.

For any subject demonstrating continued noncompliance of study drug dosing despite continued educational efforts, the Investigator should contact the study medical monitor to discuss possible discontinuation of the subject from the study.

## 5.8 Concomitant Medications

Subjects taking UDCA at the start of the study must remain on the same dose of UDCA throughout the 12-week dosing period. If the Investigator believes that dosing with UDCA should be stopped due to adverse reactions, then the Medical Monitor should be consulted prior to discontinuing the drug. Subjects who were not taking UDCA at the start of the study will not be allowed to initiate treatment during the study.

All subjects enrolled in the study must abstain from taking any prohibited concomitant medication through the end of study.

Details of prior and concomitant medication use will be recorded in the source documentation and the electronic case report form (eCRF) as indicated in the SoA (Appendix 1).

### 5.8.1 Co-administration of EDP-305 and Ursodiol (ursodeoxycholic acid, UDCA)

Drug-drug interaction between EDP-305 and UDCA is not anticipated based on available EDP-305 drug-drug interaction (see Section 1.4.2), and on UDCA metabolic profile from the literature. In the liver, ursodiol is conjugated with glycine or taurine, then secreted into bile. These conjugates of ursodiol are absorbed in the small intestine by passive and active mechanisms. The conjugates can also be deconjugated in the ileum by intestinal enzymes, leading to the formation of free ursodiol that can be reabsorbed and re-conjugated in the liver. Nonabsorbed ursodiol passes into the colon where it is mostly 7-dehydroxylated to lithocholic acid. Some ursodiol is epimerized to chenodiol (CDCA) via a 7-oxo intermediate. Chenodiol also undergoes 7-dehydroxylation to form lithocholic acid. These metabolites are poorly soluble and excreted in the feces. A small portion of lithocholic acid is reabsorbed, conjugated in the liver with glycine, or taurine and sulfated at the 3 position. The resulting sulfated lithocholic acid conjugates are excreted in bile and then lost in feces (*Axcan Scandipharm Inc., 2007*).

As UDCA is primarily metabolized through conjugation, EDP-305 is not expected to have an impact on the metabolism of UDCA.

Available data from Study EDP 305-005 indicated that CYP3A4 is a major pathway for EDP-305 metabolism, as is also supported by preclinical phenotyping data (refer to the Investigator's Brochure for additional detail). As reported in the literature, UDCA did not have an effect on midazolam pharmacokinetics (a sensitive CYP3A4 substrate) (*Becquemont et al., 2006; Dilger, Denk, Heeg, & Beuers, 2005*). [REDACTED]

[REDACTED] UDCA had limited effect on digoxin (a sensitive P-gp substrate) (*Becquemont et al., 2006*). Based on this information, UDCA is not expected to have an effect on EDP-305 pharmacokinetics during co-administration.

### 5.9 Prohibited Medications

[REDACTED]

[REDACTED]

[REDACTED]

Use of a new statin regimen is prohibited from Screening and throughout study duration. Subjects on a stable dose of statins for at least three months prior to Screening are allowed. However, no dose modification during the study will be allowed.

### 5.10 [REDACTED]

[REDACTED]

[REDACTED]

[REDACTED]	[REDACTED]	
[REDACTED]	[REDACTED]	[REDACTED]
[REDACTED]	[REDACTED]	[REDACTED]
[REDACTED]	[REDACTED]	[REDACTED]
[REDACTED]	[REDACTED]	[REDACTED]
[REDACTED]	[REDACTED]	[REDACTED]
[REDACTED]	[REDACTED]	[REDACTED]
[REDACTED]	[REDACTED]	[REDACTED]
[REDACTED]	[REDACTED]	[REDACTED]
[REDACTED]	[REDACTED]	[REDACTED]
[REDACTED]	[REDACTED]	[REDACTED]

## 6. BLINDING

The study will be double-blinded meaning the subjects, Investigators, and site staff will be blinded to treatment assignment until the completion of the study.

All study personnel will be blinded to treatment assignment except for the following individuals:

- Unblinded Enanta/CRO statistician for purpose of generating and monitoring the randomization list
- Unblinded Drug Supply Chain personnel for the purpose of monitoring drug supplies
- Enanta/CRO Pharmacovigilance Group and Regulatory Affairs representatives when required to satisfy regulatory reporting requirements
- Bioanalytical Laboratory for the purpose of measuring drug concentrations

### 6.1 Blinding of Study Samples

#### 6.1.1 Blinding of Biomarker, Fibrosis and Inflammatory Markers and Laboratory Liver Test Results

Investigators, site personnel and CRO/Sponsor will be blinded to the following laboratory tests post-Baseline:

- Biomarker laboratory data
  - FGF19,
  - total bile acids (BA),
  - C4 [7 $\alpha$ -OH-4-cholesten-3-one],
- Fibrosis and inflammatory markers
  - ELF Panel (ie, hyaluronic acid [HA], procollagen III amino terminal peptide [PIIINP], and tissue inhibitor of metalloproteinase 1 [TIMP-1])
  - PRO C3
  - Fibrinogen, CRP, alpha2 macroglobulin and haptoglobin
  - Tumor necrosis factor alpha and beta (TNF- $\alpha$  and  $\beta$ )
  - Interleukin (IL)-6, IL1 $\beta$
  - AST to Platelet Ratio Index (APRI)
  - Fibrosis 4 (FIB-4) Index
- Liver Tests
  - ALP

### 6.1.2 Blinding of Pharmacokinetic Samples

All PK sample concentration measurements will be blinded to the Investigators, site staff, and study subjects. The laboratory performing bioanalytical analysis, however, will be provided the randomization scheme.

## 6.2 Unblinding

At the initiation of the study, the study site will be instructed on the method for breaking the blind. The unblinding method will use the IWRS process.

Unblinding of individual subject treatment by the Investigator should be limited to medical emergencies or urgent clinical situations in which knowledge of the subject's study treatment is necessary for clinical management. In such cases, the Investigator must first attempt to contact the study Medical Monitor to discuss and agree to the need for unblinding. In situations in which the Investigator has attempted and failed to contact the Medical Monitor, and/or the urgency of the case required immediate action, he/she should use his/her best judgment, based on the nature and urgency of the clinical situation, and proceed with unblinding.

- [REDACTED]
- [REDACTED]

Once a subject's treatment assignment has been unblinded for a medical emergency or urgent clinical situation, the Medical Monitor and study coordinator should be notified within 24 hours of unblinding of the treatment. Information relating to unblinding (the reason, date, etc.) should be clearly recorded in the subject's study file. In addition, the Investigator should consider whether the clinical event that prompted unblinding should be considered a serious adverse event (SAE), according to the regulatory definitions or criteria for SAEs, and if so, submit an SAE report as described in Section 9.2.

CRO pharmacovigilance will also unblind any SAE reports in compliance with Regulatory reporting requirements. In addition, Enanta may unblind individual subjects at any time for matters relating to safety concerns.

## **7. STUDY CONDUCT AND VISIT SCHEDULE**

### **7.1 Study Visits**

Details of assessments at each visit are presented in the SoA (Appendix 1).

#### **7.1.1 Screening**

Screening procedures will occur after the subject signs and dates an Institutional Review Board (IRB) or Ethics Committee (EC) approved ICF and provides authorization to use protected health information (See Section 12.1.3). The ICF will be completed prior to conduct of any study-specific procedures.

Screening procedures will be conducted as listed in the SoA (Appendix 1). Screening will occur over a period lasting no more than 28 days. For each subject, Screening can occur on one day or over multiple days. All Screening assessments must occur no earlier than 28 days before the first dose of study drug at the Day 1 visit. If any Screening assessment falls outside of that window, the Investigator should consult with the Sponsor's Medical Monitor to determine if the assessment needs to be repeated.

If a subject does not qualify for study entry due to an out-of-range lab value that is not consistent with the subject's medical history or appears spurious, with the approval of the Medical Monitor, the subject may retest that lab parameter once if the Investigator believes that he/she would qualify upon retest.

At the completion of Screening procedures/assessments, subjects who qualify for the study should be given detailed instructions on fasting requirements prior to the first dose and when to return to the clinic for the Day 1 visit.

#### **7.1.2 Rescreening**

Subjects who met all eligibility criteria that were current at the time of their Screening Visit may be re screened under the following circumstances and with the approval of the medical monitor:

- Subjects within the Screening Period who met all eligibility criteria, but are not able to obtain required documentation within the allotted window for the Screening Period.
- Subjects who are eligible, but transiently (for personal reasons) unable to commit to all study procedures

#### **7.1.3 Baseline Visit (Day1)**

Subjects who meet all inclusion criteria and none of the exclusion criteria will report to the clinic on the morning of Study Day 1 after fasting overnight for a minimum of 8 hours. After a review

of applicable inclusion/exclusion criteria, subjects who continue to satisfy eligibility requirements will be randomized in a 3:3:1 ratio to their treatment group. Predose assessments and procedures will be conducted as noted in the SoA (Appendix 1) and considered Baseline values.

After predose/Baseline study procedures are completed, subjects will receive the first dose of study drug in the clinic on Day 1 followed by PK and biomarker blood draws. Additional PK, C4, FGF19 and Bile Acid samples will be collected from subjects at a subset of sites (PK/PD Substudy) that have the technical capability to collect and process intensive (longer duration) sampling. PK and PD samples will be collected as described in Section 8.4.

Before leaving the clinic, subjects will receive study medication and instructions on how to take the medication at home.

#### **7.1.4 Treatment Period Visits (Day 3, Weeks 2, 4, 8 and 12 /EOT)**

Except for days when there is a clinic visit, subjects will take their daily dose of study drug at home for 12 weeks. Throughout the 12-week treatment period, subjects will return to the clinic as shown in the SoA (Appendix 1) for study assessments. Prior to each visit, subjects will be instructed to fast for a minimum of 8 hrs prior to the scheduled visit time.

At the end of the treatment period, subjects will complete the EOT visit. Subjects who complete 12 weeks of treatment will complete the EOT assessments at the Day 84 visit/Week 12. Subjects who discontinue treatment early should complete EOT assessments at the time of discontinuation (if in the clinic) or as soon thereafter as possible if the subject discontinues treatment while not in the clinic. Procedures performed are specified in the SoA (Appendix 1).

Population PK and PK/PD samples will be collected as specified in the SoA (Appendix 1) and as described in Section 8.4.

Subjects should discontinue drug on Day 84. Subjects, who return for their EOT Visit after Day 84, should stop dosing on Day 84 (Week 12 Visit).

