### 8.3.4 Biomarkers

See Table 14 for full list of biomarkers to be collected in this study.

Fasting serum or plasma samples should be collected before the daily dose of study drug for analysis of FGF19, bile acids, and C4 at visits indicated in the SoA (Appendix 1) at Day 1, and Week 2, 4, 8 and 12 after a fast of a minimum of 8 hours.

For all subjects, samples for FGF19, bile acids, and C4 will be collected predose at the noted visits as indicated in the SoA (Appendix 1).

**PK/PD Substudy (select subjects to consent to participate):** Additional samples will be collected from subjects at a subset of sites that have the technical capability to collect and process intensive (longer duration) sampling (those also collecting intensive PK) at Day 1 and Day 84 (Week 12). Biomarker samples will be collected at predose and 2, 6, and 8 hours postdose. Additionally, an ALP sample will be collected at the same time points for subjects

participating in the PK/PD substudy (ie, predose and at 2, 6, and 8 hours postdose). On scheduled visits on Week 2, 4 and 8, samples (FGF19, bile acids, C4 and ALP) will be collected at three timepoints: predose and at two timepoints postdose; the first samples collected 1 to 3 hours postdose and the second postdose samples collected at least 1 hour later. Where possible, the samples at each visit should be obtained at different times postdose relative to each other.

[REDACTED]

[REDACTED]

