## 8.4 Pharmacokinetic Samples

### 8.4.1 Collection of Pharmacokinetic Samples

Plasma samples will be collected and processed to define the PK parameters according to the procedures provided and/or approved by Enanta Pharmaceuticals, Inc. Plasma PK samples will be collected as shown in the SoA (Appendix 1). More detailed information will be given in the Laboratory Manual.

**Population PK( all Subjects):** On scheduled visits at Day 1, and Weeks 2, 4, 8 and 12, PK samples will be collected at three timepoints: predose and at two timepoints postdose; the first postdose sample collected 1 to 3 hours postdose and the second postdose sample collected at least one hour later. Where possible, the samples at each visit should be obtained at different times postdose relative to each other.

**PK/PD Substudy (select subjects to consent to participate):** Additional samples will be collected from subjects at a subset of sites that have the technical capability to collect and process intensive (longer duration) PK samples. At Day 1 and Day 84 (Week 12) PK samples will be collected at predose and 2, 6, and 8 hours postdose. On scheduled visits on Week 2, 4 and 8, PK samples will be collected at three timepoints: predose and at two timepoints postdose; the first samples collected 1 to 3 hours postdose and the second postdose samples collected at least 1 hour later. Where possible, the samples at each visit should be obtained at different times postdose relative to each other.

More detailed information will be provided in the Study Manual. It is important that the date and time of collection of each of the PK blood samples are accurately recorded in the source document. Within 8 hours postdose, an acceptable window around each PK draw is  $\pm 10$  minutes. Predose PK samples should be drawn within 30 minutes of the next scheduled dosing time. Actual date and time of PK sample collection will be recorded in the eCRF. In addition, the site should record the time of last dose taken at home prior to the visit.

PK samples may be stored and used for future metabolite identification and/or further evaluation of the bioanalytical method. These data will be used for internal exploratory purposes and will not be included in the clinical study report.

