## 14. APPENDICES

### Appendix 1: Schedule of Assessments (SoA)

Study Event	Scr.  (D-28 to -1)	Study Assessments per Planned Study Day						EOS
		D1 	D3	D14±2 W2	D28±2 W4	D56±2 W8	D84±2 EOT  /W12	D112±2 W16
ICF  ; Demography; Medical History	x							
Inclusion/Exclusion	x							
FSH  ; HIV/HCV/HBV	x							
AMA/M2/PBC-ANAb 	x							
Pregnancy Test 	x	x			x	x	x	x
Height  , Weight, BMI	x							x
PT/PTT and INR	x							x
Oral Temperature	x	x						x
Physical Exam 	x	x	x	x	x	x	x	x
Vital Signs 	x	x	x	x	x	x	x	x
ECG	x	x	x		x		x	
Safety Lab. Tests 	x	x	x	x	x	x	x	x
PBC-40 QoL		x			x	x	x	x
VAS and 5-D Itch		x			x	x	x	x
Biomarkers (FGF19, C4, BA) 		x		x	x	x	x	
CV Markers 		x		x	x	x	x	x
Fibroscan	x							
ELF panel, PRO-C3, Inflammatory Markers 	x	x					x	
APRI, FIB-4		x					x	
PK/PD Substudy (PK, C4, FGF19, BA, ALP) 		x		x	x	x	x	
Population PK Samples 		x		x	x	x	x	
Dispense Study Drug		x			x	x		
Study Drug Dosing 		daily dosing						
Drug Accountability			x	x	x	x	x	
AEs & Con Meds 	x	x	x	x	x	x	x	x

 Screening assessments should be conducted within 28 days prior to the first dose of study drug (ie, Study Days -28 to -1)

 On Day 1, all samples are to be collected predose with the exception of respective post-dose PK and PD samples

 Subjects should discontinue drug on Day 84. Subjects who return for their EOT Visit after Day 84, should stop dosing on Day 84.

 For the treatment phase, indicates number of completed weeks of treatment

 Subjects who discontinue treatment early should complete the EOT procedures as soon as possible and return 4 weeks later for the EOS visit

 Informed consent must be obtained prior to conducting any study-specific procedures or assessments

 For post-menopausal women only

 Only if historical values are not available; one test must be positive for study entry to confirm PBC diagnosis (see Inclusion Criterion #3)

 Serum pregnancy test at Screening and Baseline, and urine pregnancy testing at Baseline and all other visits. If the urine pregnancy test is positive, a serum pregnancy test should be obtained as soon as possible to confirm.

 Height should only be measured at Screening

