 Full PE at Screening and EOS; all other exams should be targeted to review of new signs and symptoms

 Vital Signs include HR, respiratory rate, and BP and will be measured once in the morning before the morning dose of study drug

 Safety laboratory tests include chemistry (including liver function tests), hematology, and urinalysis and should be collected predose at all visits; See Table 14 for details

-  Biomarkers include fasting plasma FGF19, fasting serum bile acids, fasting C4 (7 $\alpha$ -OH-4-cholesten-3-one). Samples should be collected after a minimum 8 hr fast and before the subject takes the daily dose of study drug
-  Lipids and CV risk markers to be collected are detailed in Table 14
-  Markers of inflammation include fibrinogen, CRP, IL6, IL1 $\beta$ , TNF- $\alpha$ , TNF- $\beta$ , alpha2 macroglobulin and haptoglobin (see Table 14)
-  Collect PK/PD samples after a minimum 8 hr fast and before the daily dose of study drug. PK/PD samples on Days 1 and 84 (Week 12) collected predose and 2, 6, and 8 hr postdose; Weeks 2, 4 and 8 at predose and two samples postdose; the first sample collected 1 to 3 hours postdose and the second sample at least 1 hour later.
-  PK predose samples should be collected after a minimum 8 hr fast before the daily dose of study drug. PK samples collected Day 1, Weeks 2, 4, 8 and 12 at predose and two samples postdose; the first sample collected 1 to 3 hours postdose and the second sample at least 1 hour later.
-  Study drug given in the clinic on days where subject is seen in the clinic
-  Additional samples may be collected to further assess safety events e.g. pruritus
- [REDACTED]

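### The Week 12 window runs to Day 86 but dosing ends on Day 84, so a PK/PD substudy subject seen in window on Day 85 or 86 has no steady-state postdose profile

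*Protocol*

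**What the plan says.** **Visit window.** The Week 12/EOT column of the Schedule (Protocol Appendix 1) is Day 84 ± 2. The rows for the PK/PD substudy and population PK sit in that column and have no narrower window of their own.

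**End of dosing.** Protocol 7.1.4: "Subjects, who return for their EOT Visit after Day 84, should stop dosing on Day 84 (Week 12 Visit". Schedule footnote 3 repeats it: "Subjects who return for their EOT Visit after Day 84, should stop dosing on Day 84".

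**Dosing at visits.** Section 5.7 has subjects dose at home except when drug is "administered in the clinic (ie, at the Days 1 and 3, and Weeks 2, 4, 8 and 12 visits". Footnote 19 is broader: "Study drug given in the clinic on days where subject is seen in the clinic". The synopsis says the same of the daily dose on clinic-visit days. None of the three excepts a late EOT visit.

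**Sampling.** For the substudy, section 8.4.1 states: "At Day 1 and Day 84 (Week 12) PK samples will be collected at predose and 2, 6, and 8 hours postdose". Section 8.3.4 does the same for FGF19, C4 and bile acids on those two days: "Biomarker samples will be collected at predose and 2, 6, and 8 hours postdose". At Weeks 2, 4 and 8 substudy subjects have one predose and two loosely timed postdose samples. Subjects outside the substudy have that sparse PK schedule on Day 1 and at Week 12 too. Section 8.4.1 defines the trough sample by the dose that follows: "Predose PK samples should be drawn within 30 minutes of the next scheduled dosing time". It also asks that dosing history be kept: "In addition, the site should record the time of last dose taken at home prior to the visit".

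**Analysis.** SAP 6.3 assigns everything from Day 71 to 7 days after end of treatment to Week 12. SAP 9.3.1.1 computes PK parameters on Day 1 and Day 84 only. SAP 9.3.2.1 fits an ANCOVA to Week 12 changes in FGF19 and C4 AUC0-8 and AUC2-8. SAP 9.3.1.3 plots mean predose concentrations by visit, and SAP 9.3.3.2 correlates predose Week 12 concentrations with laboratory and PD changes.

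**The concern.** Days 85 and 86 are permitted visit days with no permitted dose. The sampling plan for that visit is written around a dose, and three other places in the protocol say that one is given. A site that follows 7.1.4 cannot collect the 2, 6 and 8 h samples. For a substudy subject that removes the only full profile after repeated dosing, because the other full profile follows the first dose.

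There is also a labelling problem. A concentration drawn on Day 86 has had an extra day of elimination, but nothing in SAP 9.3 keeps it out of the outputs headed predose at Week 12.

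**Working it through.** The plan states no figure on this point, so there is none to reproduce. The check is calendar arithmetic plus first-order decay.

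**1. Calendar.** Day 84 ± 2 covers Days 82, 83, 84, 85 and 86, so 2 of 5 permitted days follow the last permitted dose. The stop rule fits the rest of the plan: Days 1 to 84 are 84 doses, three 4-week supplies (5.7.1) are 3 × 28 = 84, and 84 + 28 = 112 is the EOS day.

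**2. What late samples would be.** Assume the last dose is taken on the morning of Day 84. Hours since that dose at the nominal 0, 2, 6 and 8 h draws are 24 × (day − 84) + h:

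| Visit | 0 h | 2 h | 6 h | 8 h |
|---|---|---|---|---|
| Day 85 | 24 | 26 | 30 | 32 |
| Day 86 | 48 | 50 | 54 | 56 |

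None of these is a 0-8 h postdose profile. Cmax, Tmax, AUClast, AUC0-8 and AUC2-8 at Week 12 are then unobtainable as defined. If a site draws at nominal clock times anyway, SAP 9.3 has no rule that keeps those values out of the AUCs.

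**3. Trough size.** Inputs: multiple-dose half-life of 10-23 h (Protocol 1.4.1, Study EDP 305-001) and monophasic decline (same section, reported after single doses). Ratio to a 24 h trough = 0.5^((t − 24)/half-life).

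- Day 85, t = 24: ratio 1. This is an ordinary trough.
- Day 86, t = 48: 0.5^(24/10) = 0.189 and 0.5^(24/23) = 0.485, that is 19% to 49%.

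**4. Effect on the predose plot.** If a fraction f of an arm is seen on Day 86, the plotted mean falls by f × (1 − ratio). The documents give no f. For each assumed 10%: 0.10 × (1 − 0.189) = 8.1% and 0.10 × (1 − 0.485) = 5.1%.

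**5. Effect of lost profiles.** The standard error of an arm mean rises by √(n/(n − k)) − 1 when k of n profiles are lost. The only stated n is the minimum of 10 per group (Protocol 5.6).

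| n in arm | k = 1 | k = 2 |
|---|---|---|
| 10 (stated minimum) | 5.4% | 11.8% |
| 30 (assumption) | 1.7% | 3.5% |

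The 30 assumes that 3:3:1 holds inside the substudy with 10 on placebo: 30 + 30 + 10 = 70, or 70/119 = 59% of planned enrolment. A treatment difference suffers less than the affected arm. With 30 versus 10 and two placebo profiles lost, √[(1/30 + 1/8)/(1/30 + 1/10)] − 1 = 9.0%.

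The effect on predose FGF19, C4 and bile acids cannot be sized, because the readable text gives no reversion time for them.

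**The case against.** The best reply is that the conflict is thin. The Day 84 stop is specific, appears twice, and agrees with a 12-week treatment and an 84-dose supply. Section 5.7 and footnote 19 are general rules on where a dose is taken. That largely stands: a reader might infer that sites do not know whether to dose on Day 85 or 86, but the specific rule mostly answers that. It does not rescue the profile, because the rule that settles dosing is the one that removes the postdose samples.

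A second reply is that 8.4.1 and footnote 17 already tie the intensive profile to Day 84. They name the day, but the Schedule column carrying the substudy row allows ± 2, and neither document says what to do when the visit is late.

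A third reply concerns importance. A reader might infer that the FGF19 and C4 secondary endpoints at Week 12 are at risk. The documents do not support that. Protocol 2.2.2 names the markers at Week 12 and not the AUCs, and fasting predose samples from all subjects serve that endpoint whether or not a dose follows. The PK endpoints name no visit, and Day 1 still supplies them. PK parameters are summarized descriptively only.

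On the trough, a Day 86 sample does not meet the protocol's own definition of predose, and SAP concentration tables are already split by hours since last dose. Both are correct. What remains is the plot and the correlations, where the SAP does not carry the definition over.

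**Conclusion.** The point holds as a small scheduling gap. An in-window visit on Day 85 or 86 leaves a substudy subject without the only intensive steady-state profile, and leaves a subject outside the substudy without two Week 12 postdose PK samples. A Day 86 concentration at 19-49% of trough can enter outputs labelled predose. The reach is the substudy AUC outputs, the predose plot and the predose Week 12 concentration correlations.

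The size depends on an attendance rate that the documents do not give and on the substudy split, where only the minimum of 10 per group is stated. SAP section 5 speaks of balance between groups in the substudy, so 30/30/10 is one possibility and not a consequence of the plan. The half-life comes from healthy volunteers and subjects with presumptive NAFLD dosed with a suspension, so the trough ratios are indicative for PBC patients on tablets.

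It would be wrong to extend this to the primary endpoint. The ALP sample for that analysis is a predose draw, is still taken, and stays inside the Week 12 window.

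**What to change.** 1. **Protocol 7.1.4 and Schedule.** For PK/PD substudy subjects, hold the intensive Week 12 visit on Day 82-84 (Day 84 −2/+0), so that the dose and the 2, 6 and 8 h samples take place in the clinic. Keep Day 84 ± 2 for all other Week 12 assessments, so that a Day 85-86 visit stays in window for ALP and for the Per Protocol set. Add *up to and including Day 84* to section 5.7 and footnote 19, and align the synopsis.
2. **SAP 9.3.** Use the recorded last-dose time to leave concentrations drawn about 48 h after the last dose (Day 86) out of the trough plot and the predose Week 12 concentration correlations, and list them separately. Day 85 samples stay in.
3. **PD ANCOVA.** Keep it on all windowed samples, as randomized. A sensitivity run limited to samples within about 30 h of the last dose is optional. The cut-off is a convention: at 30 h the concentration is 0.5^(6/10) = 66% to 0.5^(6/23) = 84% of the 24 h trough.

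Cost: a scheduling note, a few words in the protocol and one SAP sentence, with no new data. Substudy subjects have 3 permitted days instead of 5 for the intensive visit. One who can attend only on Day 85-86 still has no profile, so the change makes the loss less likely but does not rule it out. Dosing through Day 86 instead would keep the full window, but could need up to two tablets beyond the 84 implied by the supply schedule; bottle contents are redacted.
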